6. INVESTIGATIONAL PRODUCTS

The Investigational Products will be made available by the study coordinator (FSNN).

Protocol Number: FSNANO08032022 -2.0 amendment 1 Date: 20032023	
STUDY Code: N-HANCE	Page 11 of 26

6.1 Name and Description of the Investigational Product

N-Pep-12 (Cebrium/MemoProve)

6.2 Dosage, Formulation and Administration

Active Treatment - N-Pep-12: 45 mg / 90mg

Placebo: Lactose

6.3 Packaging and Labelling

The investigational product and the reference product will be packaged and labeled for use in clinical trials according to GMP Annex 13 and local legislation.

6.4 Storage

The study medication will be stored at room temperature in a dry place. All supplies must be kept in a locked place, inaccessible to unauthorized persons until they are delivered to the individual patient.

6.5 Investigational Product Accountability and Destruction

The amount of used medication will be recorded in the CRF. All unused medication will be counted and documented and unused investigational products will be destroyed upon completion of accountability.

7. CONCOMITANT MEDICATION

All previous and concomitant medication must be included in the CRF, including the starting date, stop date (if applicable), highest total daily dose, and method of administration. Moreover, the reason (diagnosis) for receiving a specific concomitant treatment must be documented. Finally, if a concomitant drug is administered as a preventive treatment, it must be noted on the CRF page for that medication.

8. DEFINITION OF THE PRIMARY AND SECONDARY VARIABLES

8.1 Primary Variables

8.1.1 Test of Attentional Performance (TAP)

The Test of Attentional Performance (TAP) is a software package that may be used to test attention skills in adults and children, as well as aspects of visual perception. The test battery comprises of a number of different tests that allow for a more detailed examination of the various aspects of attention. Norm values are provided for the interpretation of the results, taking into account age, gender, and education. The design of these tests was primarily driven by the needs of neuropsychological diagnostics, which place unique demands on appropriate test procedures due to the sometimes high specificity of the deficits as well as the patients' frequently present numerous impairments (Zimmerman & Fimm, 2022).

8.1.1.1 Alertness Subtest

For the Alertness (phasic alertness) subtest, the reaction time is tested under two conditions. The first

Protocol Number: FSNANO08032022 -2.0 amendment 1 Date: 20032023	
STUDY Code: N-HANCE	Page 12 of 26

condition involves simple reaction time measurements in which a cross appears on the monitor at irregular points and the subject must respond as quickly as possible by pressing a key (Zimmerman & Fimm, 2022).

8.1.1.2 Working Memory Subtest

The task investigates information flow control and the updating of information in working memory. On the monitor, the subject is shown a series of numbers. The subject must determine whether each number corresponds to the previous number or the one before that, depending on the condition (Zimmerman & Fimm, 2022).

8.1.1.3 Divided Attention Subtest

A visual and an auditory task must be completed concurrently in this test. The tasks focus on attentional selectivity, focused attention and visuo-spatial attention (Zimmerman & Fimm, 2022).

8.2 Secondary Variables

8.2.1 Wechsler Adult Intelligence Scale (WAIS-IV) - Digit Span Forward, Backward (DSF, DSB)

The Digit Span task exercises a patient's verbal working memory. Attention and comprehension also contribute to performance. The digit span task is also closely related to language learning abilities. The procedures for assessing working memory are widely accepted. A list of numbers is read aloud at a rate of one per second, and the participant is then asked to recall the numbers in the correct order. The first list starts with three numbers and grows until the person starts making mistakes. plus or minus two numbers. This test can be distributed both backward and forwards. Scores are thought to correlate with age and not intelligence (Wechsler, 2008).

8.2.2 Perceived Stress Scale (PSS)

The Perceived Stress Scale (PSS) is the most commonly used psychological tool for assessing stress perception. It's a metric for how stressful certain situations in one's life are regarded. Items were chosen to reflect how unexpected, unmanageable, and overburdened respondents' lives are. A number of direct questions about current levels of experienced stress are also included on the scale. The PSS was created with at least a junior high school education in mind for use in community samples. The items are straightforward, and the response options are concise. Furthermore, the questions are of a general nature and hence lack the substance that is specific to any demographic group. The PSS questions inquire about feelings and ideas from the previous month. Respondents are asked how often they feel a certain way in each situation (Cohen, 1994).

8.2.3 Brief Mood Introspection Scale (BMIS)

The Brief Mood Introspection Scale (BMIS) is an open-source mood scale that uses 16 mood adjectives like "glad" and "fed up" to score participants' present mood state. The 16-item Brief Mood Introspection Scale (BMIS) was created as a subset of the Mood-State Introspection Scale, which has 62 items. Both subtractive and reverse scoring are used to score the BMIS. Although subtractive scoring was indicated in the original article containing the BMIS, reverse scoring is now the preferred method of scoring the test. Reverse scoring is the process of locating items on a scale that measure the polar opposite of the dominant end (for example,

Protocol Number: FSNANO08032022 -2.0 amendment 1 Date: 20032023	
STUDY Code: N-HANCE	Page 13 of 26

"Unpleasant" Items on a Pleasant Unpleasant Mood scale) and then reversing the scale values for those opposite items (Mayer & Gaschke, 1988).

8.2.4 Sleep Quality Scale (SQS) / Subjective, patient questionnaire

The SQS is a 28-item questionnaire that assesses six different aspects of sleep quality: daytime symptoms, sleep restoration, issues initiating and maintaining sleep, trouble waking, and sleep enjoyment. The goal of the developers was to construct a scale that could be used as a broad, efficient metric for measuring sleep quality in a variety of patient and research populations. The scale has been validated in individuals aged 18–59 years and it only requires 5-10 minutes to complete, being a straightforward self-reporting, pencil-and-paper test (Shahid, Wilkinson, Marcu, & Shapiro, 2011).

8.2.5 EQ-5D-5L

The EQ-5D-5L is divided into two sections: the description system and the visual analog scale. The five dimensions of the descriptive system are mobility, self-care, typical activities, pain/discomfort, and anxiety/depression. For each dimension, there are five levels: no issues, mild issues, moderate issues, severe issues, and extreme issues. The patient is asked to check the box next to the most appropriate statement in each of the five aspects to reflect his or her health status. A one-digit number reflecting the level chosen for that dimension is the result of this selection. The digits of the five dimensions can be added together to create a five-digit number that indicates the patient's health state (Herdman et al., 2011).

9. ASSESSING AND REPORTING OF ADVERSE EVENTS

Throughout the course of the clinical study particular attention is paid to the Adverse Events and Adverse Drug Reactions mentioned below.

9.1 Adverse Events (AE)

Any adverse medical event in a patient or clinical trial subject who has received a pharmaceutical product that does not necessarily have a causal relationship with this treatment is referred to as a Serious/Adverse Event (S/AE). Any undesirable and unanticipated sign (including an abnormal laboratory finding), symptom, or disease that is temporally connected with the use of an Investigational Product, whether related or not, is referred to as an adverse event (AE).

9.2. Adverse Drug Reaction (ADR)

All unanticipated and undesirable reactions to an Investigational Product caused by any application or dose given. The phrase "responses to an Investigational Product" refers to a causal relationship that has been determined by either the Investigator or the Coordinator. Reasonable implies that there is a hint or argument that a causal relationship exists. In the case of commercialized Investigational Products, an unpleasant and unanticipated reaction to a product happens in applications that are often utilized in man for disease prevention, diagnosis, or therapy, or to affect physiological function.

9.2.1 Serious Adverse Event or Serious Adverse Reaction (SAE/SAR)

Protocol Number: FSNANO08032022 -2.0 amendment 1 Date: 20032023	
STUDY Code: N-HANCE	Page 14 of 26

Serious Adverse Events will be considered for AE documentation due to the patient's underlying constitution. Serious Adverse Drug Reactions will be handled as outlined below.

Expedited Reporting is required if the following criteria apply (ICH E2A):

1. Serious
2. Unexpected
3. A reasonable causal relationship to study treatment.

An Adverse Drug Reaction is considered serious if it:

- Results in Death
- Is life-threatening
- Requires additional inpatient hospitalization or prolongation of existing Hospitalization
- Results in persistent or significant disability/incapacity
- Results in a congenital anomaly or birth defect
- Other medically significant events that require immediate medical or surgical Intervention

Unexpected means:

- Not consistent with Investigators Brochure or SmPC

Causal Relationship means:

- There are facts/evidence to suggest a causal relationship
- As judged by the reporting health care professional to have a reasonable suspected causal relationship

NOTE

Death: is the result of an Adverse Event The medical condition that caused death, such as an underlying disease or an accident, must be reported in detail

Life-threatening: in the definition of a Serious Adverse Event or Adverse Reaction refers to an event in which the patient was at risk of death at the time of the event; it does not refer to an event which hypothetically might have caused death if it was more severe

In some circumstances, medical judgment should be utilized to determine the seriousness of an Adverse Event / Reaction. Important Adverse Events / Reactions that are not immediately life-threatening or do not result in death or hospitalization but may put the patient at risk or demand intervention to avoid one of the other outcomes specified in the description above may also be deemed serious.

9.3. Suspected Expected Serious Adverse Reaction (SESAR)

Any adverse reaction that is classed in nature as serious and which is consistent with the available information on the medicinal product in question set out in the SmPC.

Protocol Number: FSNANO08032022 -2.0 amendment 1 Date: 20032023	
STUDY Code: N-HANCE	Page 15 of 26

9.4. Suspected Unexpected Serious Adverse Reaction (SUSAR)

Any adverse reaction that is classed in nature as serious and which is **not** consistent with the available information on the medicinal product in question set out in the SmPC.

9.5. Recording of Adverse Events

All adverse events, whether serious or not, will be documented and reported in compliance with the definitions previously provided.

The Investigator must record all adverse signs and symptoms that are either volunteered by patients or seen during or after the administration of the Investigational Product on the corresponding CRF page.

The description should include the nature of the sign or symptom, the date of onset, the date of resolution (duration), the severity/intensity, the relationship to study treatment or other therapy, the action taken (if any), and the outcome.

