Visit Schedule	
Visit 1 - Screening Study day 0
 
 • Demographic data • Medical history and risk factors • ICF • Randomization • Primary and secondary outcomes 
Visit 2 - Efficacy Evaluation Study day 30
 
 • Primary Outcomes • Secondary Outcome 
Visit 3 - Efficacy Evaluation Study Day 90
 
 • Primary Outcomes • Secondary Outcome

Protocol Number: FSNANO08032022 -2.0 amendment 1 Date: 20032023	
STUDY Code: N-HANCE	Page 7 of 26

	Visit 4 - Efficacy Evaluation Study Day 180
	
 • Primary Outcomes • Secondary Outcome
Active dietary supplementation arms	N-Pep-12 (45 mg), daily (Day 0-Day 180) N-Pep-12 (90 mg), daily (Day 0-Day 180)
Reference Product	Placebo – Lactose (Day 0-Day 90)

*All treatment cycles and efficacy evaluations will be performed within a window of ± 3 working days

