4. STUDY DESIGN

Randomized, placebo-controlled, double-blind

N-PEP-12 groups shall be tested against Placebo. The 3 groups are:

Study Group 1: 45mg N-PEP-12

Study Group 2: 90mg N-PEP-12

Study Group 3: Placebo (Lactose)

The trial will be conducted in a sample of healthy middle-aged and older adults, with subjective cognitive function complaints. The study extends over an observation period of 180 days. Four visits for clinical evaluation are planned as follows:

Visit 1 - (Study day 0) - Screening - will consist of the baseline assessment - demographic data and the patient's medical history and risk factors will be collected. Also, the informed consent will be signed and the patient will be randomized. **Visit 2 - (Study day 30)** will be an efficacy evaluation. Between Visit 1, Visit 2 and **Visit 3 - (Study day 90)** patients shall receive their treatment, based on the group they have been allocated at baseline: Placebo, 45mg N-PEP-12 or 90 mg N-PEP-12. Between Visit 3 and **Visit 4 - (Study day 180)** the patients shall continue the treatment with the two N-PEP-12 groups unchanged and the initial Placebo group receiving 90 mg N-PEP-12.

All treatment cycles and efficacy evaluations will be performed within a window of ± 3 working days.

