9.8 Adverse Event/Reaction follow-up procedure

Adverse Events/ Reactions will be followed up throughout the course of the clinical study and any changes will be recorded in the CRF.

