10. STUDY SCHEDULE

10.1 Procedures at Each Visit

Visit 1 - Screening - Study day 0

- Demographic data
- Medical history and risk factors
- ICF
- Randomization
- Primary and secondary outcomes

Visit 2 - Efficacy Evaluation -Study day 30

- Primary Outcomes
- Secondary Outcome

Visit 3 - Efficacy Evaluation -Study Day 90

- Primary Outcomes
- Secondary Outcome

Visit 4 - Efficacy Evaluation - Study Day 180

- Primary Outcomes
- Secondary Outcome

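### Adverse events reach the record only if volunteered or seen, and no scheduled visit lists asking about them, so a low recorded rate could not be told apart from not asking

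*Protocol*

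**What the plan says.** **Recording rule.** Section 9.5 opens with a general duty: "All adverse events, whether serious or not, will be documented and reported in compliance with the definitions previously provided". It then says how events reach the case report form. The investigator is to "record all adverse signs and symptoms that are either volunteered by patients or seen during or after the administration of the Investigational Product". The entry must also give onset and resolution dates, intensity, relationship to treatment, action taken and outcome.

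**Follow-up.** Section 9.8 says events "will be followed up throughout the course of the clinical study" and that changes go into the case report form.

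**Visits.** The synopsis and section 10.1 agree. Visits 2, 3 and 4 (Days 30, 90 and 180) are efficacy evaluations listing primary and secondary outcomes and nothing else. The last is headed "Visit 4 - Efficacy Evaluation - Study Day 180".

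**Exposure.** The synopsis gives active dosing as, for example, "N-Pep-12 (90 mg), daily (Day 0-Day 180". Section 4 sets an observation period of 180 days and, for the time after Visit 3, has "the initial Placebo group receiving 90 mg N-PEP-12".

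**Use of the data.** Section 12 defines a safety population and says it will be used for the safety analysis.

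**The concern.** The protocol promises complete documentation, but the only method it states is passive. What patients volunteer depends on what they remember and think worth raising, up to 90 days later. What staff can see is limited when the product is a capsule or tablet taken daily between four visits. Neither schedule gives staff a written prompt to ask.

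At stake is the meaning of the safety result. Events that were never recorded cannot be recovered in the analysis, so this cannot be left to the statistical analysis plan. If the report shows few events, a reader could not tell whether few occurred or few were mentioned. The schedule also ends on the day dosing ends, while sections 9.5 and 9.8 ask for information that often becomes available only later.

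**Working it through.** The plan states no figure to reproduce. The check sets passages side by side and does day arithmetic on the schedule.

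**1. Routes into the record.** Section 9.5 names two: volunteered and seen. No question, checklist, diary or telephone call appears in section 9 or section 10. The definition in section 9.1 is wider than either route suggests, since it covers signs, symptoms and disease, "including an abnormal laboratory finding".

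**2. What the visits list.** Visits 2, 3 and 4 list primary outcomes and secondary outcomes in both schedules. Adverse-event items listed: 0 of 3 post-baseline visits. Concomitant medication, which section 7 requires with dates and reasons, is not listed either.

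**3. Intervals between scheduled contacts** (Days 0, 30, 90, 180):
- Visit 1 to 2: 30 − 0 = 30 days
- Visit 2 to 3: 90 − 30 = 60 days
- Visit 3 to 4: 180 − 90 = 90 days

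Participants who start 90 mg at Day 0 have their first scheduled visit on that dose after 30 days. The initial placebo group, starting 90 mg at Day 90, has it after 180 − 90 = 90 days.

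**4. Time after the last dose.** Last scheduled visit minus last planned dosing day: 180 − 180 = 0 days. The window of ±3 working days applies to treatment cycles as well as evaluations. It may move Visit 4 slightly but creates no follow-up period.

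**5. What the protocol asks for against what the schedule can supply.**

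| Required | Source | Scheduled contact that supplies it for an event open at, or starting after, Day 180 |
|---|---|---|
| Events seen after administration | 9.5 | none |
| Resolution date and outcome | 9.5 | none |
| Response to withdrawal (for the definite and probable grades) | 9.5.2 | none |

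**6. Size of the under-recording.** Recorded rate = true rate × fraction captured. The protocol gives neither the true rate nor the captured fraction, so the product cannot be computed. The direction is clear: any fraction below 1 lowers the recorded rate.

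**The case against.** **The protocol does not forbid asking.** Section 9.5 says all events will be documented, section 9 opens by promising particular attention to them, and the case report form page, which is not shown, may carry a prompt. This stands in part. The fair statement is that no method of asking is stated, not that asking is excluded.

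**The visit list is not exhaustive.** It also omits concomitant medication, product accountability and compliance, all required elsewhere. A reader might infer from section 10.1 that nobody will be asked about events; the documents do not support that. They do leave asking to individual habit, because no section requires it.

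**Follow-up may outlast Day 180.** Section 9.8 runs for the course of the study, which for many participants may extend beyond their own last visit. Section 5.3.2 asks for reasonable efforts to reach patients who go missing, and section 9.6 sets a 24-hour reporting duty for serious reactions. A reader might infer that serious reactions open at Day 180 will be left without an outcome. That is not shown. What is shown is that no contact is scheduled at which the outcome would be obtained.

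**No bias between arms is demonstrated.** Up to Day 90 the same blinded procedure applies in every arm. This stands: the effect up to then is lower rates and lower sensitivity, not a demonstrated distortion of the comparison.

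**Safety is not an objective.** No primary or secondary objective concerns it. This limits the weight of the point but does not remove it, since section 12 plans the analysis.

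**Conclusion.** The point holds as a weakness in how events are collected. A rule with two passive routes, no adverse-event item at any of the three post-baseline visits, and intervals of 30, 60 and 90 days is likely to under-record events. A low rate would then not support a safety conclusion by itself. Separately, the schedule provides 0 nominal days of observation after the last planned dose, although sections 9.5 and 9.8 call for later information.

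The conclusion assumes that participants take the product away from the site. This is inferred from the oral form (section 2.1) and the small number of visits. The protocol does not state it, and section 10.2 speaks of intravenous infusions. It also assumes that the unseen case report form does not already prescribe a question.

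Two stronger readings go too far. One is a numerical estimate of the share of events lost, for which the protocol has no input. The other is that the comparison between arms is biased, which is not shown up to Day 90. The primary efficacy result is not affected.

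**What to change.** 1. **Section 9.5:** change the rule so that events are recorded when *volunteered, observed, or elicited by one standard open, non-leading question asked at every post-baseline visit by blinded staff*.
2. **Synopsis and section 10.1:** list *AE/SAE and concomitant medication review* at Visits 2, 3 and 4.
3. **Sections 9.5 and 9.8 against the schedule:** reconcile the call for events after administration, resolution dates and outcomes with a last scheduled contact on the last planned dosing day. Otherwise, state in the report that the safety data do not cover the time after the last dose.

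**Cost.** Items 1 and 2 need protocol and case report form wording and a few minutes at visits already planned. The small downside is that more minor, unspecific events will be recorded in all arms. Item 3 is wording only if the limitation is reported; following events beyond Day 180 would need contact outside the present schedule.

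**What this does not change.** The 90-day interval after the initial placebo group starts 90 mg remains, and the report should state it when describing events in that period.

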9.5.1 Definition of Adverse Event intensity

Intensity	Definition
Mild	Patient is aware of signs and symptoms, but they are easily tolerated
Moderate	Signs/symptoms cause sufficient discomfort to interfere with usual activities
Severe	Patient is incapable to work or perform usual activities

9.5.2 Definition of Adverse Event causality

The following criteria are used to indicate the degree of causation (all points should be reasonably complied with) based on the WHO-UMC system for standardized case causality assessment (www.who-umc.org):

Definite

- Event or laboratory test abnormality, with plausible time relationship to drug intake
- Cannot be explained by disease or other drugs
- Response to withdrawal plausible (pharmacologically, pathologically)
- Event definitive pharmacologically or phenomenologically (i.e. an objective and specific medical disorder or a recognized pharmacological phenomenon)
- Re-challenge satisfactory, if necessary

Protocol Number: FSNANO08032022 -2.0 amendment 1 Date: 20032023	
STUDY Code: N-HANCE	Page 16 of 26

Probable

- Event or laboratory test abnormality, with reasonable time relationship to drug intake
- Unlikely to be attributed to disease or other drugs
- Response to withdrawal clinically reasonable (for details refer to WHO-UMC)
- Re-challenge not required

Possible

- Event or laboratory test abnormality, with reasonable time relationship to drug intake
- Could also be explained by disease or other drugs
- Information on drug withdrawal may be lacking or unclear

Unlikely

- Event or laboratory test abnormality, with a time to drug intake that makes a relationship improbable (but not impossible)
- Disease or other drugs provide plausible explanations

Not related

The event does not follow a reasonable temporal sequence from the administration of the IMP and is clearly related to other factors, such as clinical state, therapeutic intervention or concomitant therapy.

Not assessable

- Report suggesting an adverse reaction
- Cannot be judged because the information is insufficient or contradictory
- Data cannot be supplemented or verified

All cases judged by any or both assessors as having a “reasonable causal relationship” to the IMP qualify as ADR. This corresponds to the categories “definite”, “probable” and “possible”.

